Randomization of the study participants is carried out on the same day or the next day after signing the informed consent, but no later than 3 days from the date of material sampling to the PCR test.

Randomization is carried out according to the Randomization List version 1.00 from 16.11.2020. To randomize a participant into a study, a research physician must contact the employee responsible for randomization (instructions for randomization are provided by the sponsor to the center before the start of the study) by phone and provide the study code and the researcher's full name for identification, as well as the data of the randomized participant: screening number, initials, date of birth. The researcher is informed of the assigned randomization number of the participant and the number of the prevention group (I or II). After the call, a Randomization Form is sent to the researcher's email as confirmation. The form must be printed out, signed by the researcher, and attached to the primary documentation of the participant.

The intake of the study drug is carried out independently by the participant at home, with the Diary of the participant of the study.

Other preventive measures

Any non-specific measures for the prevention of a new coronavirus infection COVID-19 are allowed, including personal protective equipment (respirators, glasses, gloves, protective suits).

Previous therapy

As a previous therapy, it is prohibited to take any drug with test status 1 month before participating in this study.

Concomitant therapy

According to the design of the non-interventional study, participants can receive any concomitant therapy for concomitant chronic diseases, except medications prescribed off-label or for research purposes.

Prohibited therapy

For the study group: use of any medications that may or may have preventive effects against ARVI, including COVID-19, is **prohibited**; use of non-specific methods of preventive protection is **not prohibited**.

For the control group: use of interferon gamma is **prohibited**; use of any medications that may or may have preventive effects against ARVI, including COVID-19, as well as the use of non-specific methods of preventive protection is **not prohibited**.

All preventive measures, including pharmacotherapeutic ones, should be indicated in the diary filled in by the participant.

Exclusion criteria

A participant should be excluded from the study if at least one of the following criteria is met:

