1. The use of the prohibited therapy indicated above, specific to each of the groups.
2. Withdrawal of informed consent.
3. Compliance to the study therapy is 50% or less.
4. Systematic non-compliance with protocol procedures by the participant.
5. Development of individual intolerance to the study drug (for the study group).
6. The development of concomitant diseases or conditions that, according to the researcher, may distort the results of the study, restrict the rights of the volunteer or put him at greater risk.
7. The appearance of contraindications to the use of the study drug in the period before the last intake of the second 10-day cycle (for the study group).
8. Participation in a clinical trial using a different therapy.
9. Disagreement on following reliable contraceptive measures (sexual abstinence; or a combination of 2 different methods: for example, barrier and spermicides, or barrier and intrauterine device, or barrier and hormonal, etc.) – for participants with preserved childbearing potential in the period before the last intake of the second 10-day cycle (for the study group).
10. Pregnancy.

A woman who excluded from the study due to the onset of pregnancy during the clinical trial is subject to medical supervision during the entire period of pregnancy, as well as for 6 months postpartum period to assess the condition of the woman and the born child (observation is carried out if possible and only if her desire and consent to such observation is mandatory). Information about the course of pregnancy and its outcome is entered in the primary documentation (with the consent of the woman). During the entire period of pregnancy, together with an obstetrician-gynecologist (with the consent of the pregnant woman and, if possible, contact with a doctor), observing a woman, her general condition, data reflecting the nature of the course of pregnancy, results of laboratory and instrumental examination methods, including ultrasound, are analyzed. Monitoring of the born child is carried out with the consent of the woman together with the district pediatrician (if possible, contact with him) until the child is 6 months old to analyze the clinical status of the child, data from laboratory and instrumental research methods.

There are no procedures for replacing excluded participants.

Diaries of participants

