In this study, the main parameter of effectiveness is the proportion of patients with acute respiratory viral infections, including COVID-19, at the end of the period of preventive administration of the drug. The study is planned to show that in the study group, the number of patients with acute respiratory viral infections, including COVID-19, will be significantly less compared to the control group.

The efficiency parameter was selected based on international recommendations for manufacturers of medicines and biological products [28].

The null hypothesis will be tested by comparing the number of cases in the two groups at the end of the period of preventive administration of the drug. It is expected that at least 90% of randomized patients will be suitable for inclusion in the population of the primary analysis (PP). The statistical purpose of the study is a comparative study of the effectiveness of the preventive regimen of the drug. In the main group of study I, study drug Ingaron 100,000 IU, lyophilizate, will be used to prepare a solution for intranasal administration, 1 time a day every other day for 10 days with a repeat of the 10-day course of preventive administration after 7 days of interruption.

To estimate the sample size in this study, an 80% power level was taken (P – probability of not missing the present effect is 0.8) and a one-sided level of statistical significance of 5% (α – the probability of making an erroneous decision about the presence of an effect is less than 0.05). The statistical criteria used are one-sided due to the availability of information about the superiority of the effect of the study drug over the lack of preventive measures against the nosology being studied [28].

Thus, the sample size was calculated based on the following parameters:

- at the required significance level $\alpha = 0.05$, the value of $Z = 1.96$;
- level of statistical power is assumed to be 80%, the value of $Z = 0.84$;
- method of sample formation – randomization using random elements.

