The primary criterion of effectiveness is the proportion of patients with acute respiratory viral infections, including COVID-19, at the end of the period of preventive administration of the drug (measurement time: 28 days). Secondary efficacy criteria: proportion of patients with confirmed COVID-19 at the end of the period of preventive administration of the drug (measurement period: 28 days); proportion of patients with acute respiratory viral infections, including COVID-19, at the end of the follow-up period (change period: 2 months); proportion of patients with confirmed COVID-19 at the end of the follow-up period (period of change: 2 months); and the frequency of development of complicated course of ARVI.

The literature analysis conducted on similar studies of the effectiveness and safety of the use of interferon-gamma shows that the incidence of ARVI can be observed in 2% of cases in the main group of patients taking interferon gamma, as well as in 14% of the control group taking alternative methods of protection and representing medical workers working in the "red zone" and those at high risk through frequent and prolonged contact with infected patients ($p < 0.05$).

Provided incidence in the control group is from 1 to 5% (taking into account the assumption that the incidence in the control group will be approximately equal to the average incidence of the general population) [29], and incidence in the study group will be at least 3% lower (which can already be considered a minimally clinically significant decrease in incidence in the absence of preventive measures with proven effectiveness, which could be taken as a standard), minimum sample size should be 630 patients (taking into account 10% of early retirement). Such a sample size will also make it possible to establish a decrease in incidence by 4% or more when incidence is set at up to 8% in the control group and a decrease in incidence by 6% or more when the incidence is set at up to 18% in the control group (Table 1 – Dependence of the sample size on various parameters).

The calculation of the required sample size was performed using a formula for calculating the sample size for a qualitative sign [30]:

$$n = \frac{P_1 * Q_1 * t^2 + P_2 * Q_2 * t^2}{(P_1 - P_2)^2}$$

Note to the formula:

P – proportion of cases in which the study sign occurs,

Q – proportion of cases in which the study sign does not occur,

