t – critical value of the Student's t-test at the appropriate level of significance.

Considering the ratio of the distribution of patients into groups 1:1 with the above parameters, the study should complete at least 572 patients: 286 in each group. Considering the possible 10% premature exclusion and withdrawal of informed consent, it is necessary to randomize 630 patients (315 in each group).

Below is the dependence of the sample size on the parameters of the magnitude of the expected effect and the minimum difference that needs to be detected (Table 1 – Dependence of the sample size on various parameters).

Thus, the sample size in each group with a random distribution method will be¹⁰:

Table 1 – Dependence of the sample size on various parameters

| The proportion of sick patients in the control group, % | Decreased proportion of cases compared to the control group, % | | | | | | | |
|---|--|-----|-----|-----|-----|----|----|----|
| | 2 | 3 | 4 | 6 | 8 | 10 | 12 | 14 |
| 2 | 207 | - | - | - | - | - | - | - |
| 3 | 411 | 136 | - | - | - | - | - | - |
| 4 | 613 | 227 | 101 | - | - | - | - | - |
| 5 | 809 | 315 | 151 | - | - | - | - | - |
| 6 | 1001 | 400 | 200 | 66 | - | - | - | - |
| 8 | 1373 | 526 | 295 | 109 | 48 | - | - | - |
| 10 | 1728 | 686 | 386 | 151 | 72 | 37 | - | - |
| 12 | 2066 | 840 | 473 | 189 | 95 | 53 | 31 | - |
| 14 | 2387 | 988 | 556 | 228 | 117 | 67 | 41 | 25 |

¹⁰ The calculation is given for a power of 80%, a one-sided significance level of 0.05 and taking into account 10% of the early exclusion of patients from the study

| | | | | | | | | |
|----|------|------|-----|-----|-----|-----|----|----|
| 16 | 2692 | 1126 | 634 | 263 | 136 | 80 | 51 | 33 |
| 18 | 2979 | 1257 | 707 | 297 | 156 | 92 | 59 | 40 |
| 20 | 3249 | 1382 | 777 | 329 | 175 | 106 | 68 | 46 |
| 22 | 3502 | 1498 | 843 | 359 | 193 | 117 | 76 | 53 |
| 24 | 3739 | 1607 | 904 | 387 | 209 | 128 | 84 | 58 |

Thus, in the present study, taking into account the possible 2% exclusion of patients at the screening stage due to non-compliance with the inclusion/non-inclusion criteria, it is planned to include up to 642 volunteers with a 1:1 distribution in each of the 2 parallel groups (study and control), of which up to 321 people will use study drug Ingaron with preventive objective, up to 321 people, will not use the study drug and will form a control comparison group.

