5.2. The size of the sample under study

The estimation of the sample size of subjects was based on the following parameters:

- bilateral significance level $\alpha=0.05$ Z value = 1.96;
- statistical power level is 80%, Z-value = 0.84;
- method of sample formation — randomization using elements of randomness;
- statistical criteria used are two-sided due to the lack of a posteriori information about the superiority of the effect of the study drug over the placebo effect.

Calculation results:

- number of volunteers who must complete participation in the study in accordance with the protocol is 286 in the group or a total of 572 participants.
- number of randomized participants is 315 in a group or total 630 people
- number of screened volunteers – up to 642.

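### Other preventive drugs are barred in Group I but allowed in Group II, so the randomised contrast is not the effect of Ingaron alone, to which the plan attributes any difference

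*Protocol*

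**What the plan says.** The Protocol, under Prohibited therapy, gives one rule per arm. For Group I: "For the study group: use of any medications that may or may have preventive effects against ARVI, including COVID-19, is" prohibited, while non-specific protection remains allowed. For Group II: "For the control group: use of interferon gamma is" prohibited, but "use of any medications that may or may have preventive effects against ARVI, including COVID-19, as well as the use of non-specific methods" of protection is expressly not prohibited.

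Exclusion criterion 1 ties removal from the study to these separate rules: "The use of the prohibited therapy indicated above, specific to each of the groups".

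The control arm is defined by non-use of Ingaron. Under Number of participants, its members "will not use the study drug and will form a control comparison group". SAP 2.1 says the same, and SAP 2.3 states that the study is open-label.

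Two sentences on test sidedness mention other comparators. The Protocol (Number of participants) calls its criteria "one-sided due to the availability of information about the superiority of the effect of the study drug over the lack of preventive measures". SAP 5.2 calls its criteria two-sided because information is lacking on "superiority of the effect of the study drug over the placebo effect".

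**The concern.** Randomisation here assigns two things together: Ingaron, and whether other drug prophylaxis is permitted. The Protocol's primary objective, the scientific hypothesis in SAP 3.1 and the null hypothesis in SAP 5.1 are all worded as the effect of giving Ingaron. The design does not isolate that effect.

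If some controls take other drugs that work, the control rate falls and the observed difference shrinks. A null result could then mean that Ingaron does nothing, or that the controls were protected by something else. The Protocol's Introduction says that interferons alpha and beta have antiviral activity of their own, and Group II may use them. Because the study is open-label, controls choose such products knowing their allocation. The effect estimate therefore depends on an uptake that the plan leaves open.

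**Working it through.** **1. The two rules side by side**

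| | Group I | Group II |
|---|---|---|
| Interferon gamma | assigned | prohibited |
| Any other drug with possible ARVI-preventive effect | prohibited | allowed |
| Non-specific protection | allowed | allowed |
| Consequence of taking another preventive drug | exclusion (criterion 1) | none |

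The arms differ in the first two rows. The last row means that the same co-medication removes a Group I participant and keeps a Group II participant, which also bears on who enters the PP set.

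**2. What the analysis plan does about it.** The Protocol asks for all preventive measures, drugs included, to be entered in the diary. The control diary (Appendix 2) has a table for preventive drugs. SAP 5.1 describes medications used by group. No planned analysis addresses other preventive drugs: the sensitivity populations in SAP 5.4 and 5.5 concern vaccination, and Table 6 of SAP section 6 covers only masks, respirators, gloves, glasses and overalls.

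**3. The plan's own sample size.** With the Protocol's formula, control 5%, Ingaron 2% and t = 1.96:

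n = (0.05×0.95 + 0.02×0.98) × 1.96² / 0.03² = 0.0671 × 3.8416 / 0.0009 = 286.4 per group, and 286.4 × 1.10 = 315.1.

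This reproduces the stated 286 and 315. The calculation uses a single control rate and makes no allowance for preventive drugs taken by controls.

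**4. Illustration of dilution.** Assume that 5% is the control risk without other drugs, that Ingaron gives 2%, and that a share u of controls takes a product of relative efficacy e. The documents give neither u nor e.

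Control rate p_c = 5% × (1 − u×e). With p_t = 2%, n = 286, d = p_c − p_t and p̄ the mean of the two rates:

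power = Φ{ [d√n − z√(2p̄(1−p̄))] / √(p_c(1−p_c) + p_t(1−p_t)) }, with z = 1.96 (two-sided 5%) or 1.645 (one-sided 5%).

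- No other drugs: (0.03×16.91 − 1.96×0.2599)/0.2590 = −0.008, power 49.7%.
- u = 10%, e = 20%: (0.029×16.91 − 1.96×0.2581)/0.2573 = −0.060, power 47.6%.
- u = 50%, e = 50%: (0.0175×16.91 − 1.96×0.2363)/0.2360 = −0.709, power 23.9%.

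| u | e | Control rate | Difference (points) | Power, two-sided | Power, one-sided |
|---|---|---|---|---|---|
| any | 0 | 5.00% | 3.00 | 50% | 62% |
| 10% | 20% | 4.90% | 2.90 | 48% | 60% |
| 25% | 30% | 4.63% | 2.63 | 42% | 54% |
| 50% | 30% | 4.25% | 2.25 | 34% | 46% |
| 50% | 50% | 3.75% | 1.75 | 24% | 35% |

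The starting value of about 50%, rather than the stated 80%, arises because the formula that yields 286 has no power term. That is a separate defect and is not caused by the asymmetry.

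**The case against.** Ingaron alone against self-chosen prevention is a coherent pragmatic question for an open-label post-marketing study, and randomisation still protects that comparison. If other drugs work, the bias runs against Ingaron, so the asymmetry does not manufacture a positive result. Use of other drugs is recorded in the control diary, so uptake there would be visible. All of this stands. It supports keeping the design if the sponsor wants it, but not describing the result as the effect of Ingaron as such.

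The illustration is also open to challenge. The Protocol ties its control rate to the average incidence in the general population, which may already reflect people's usual prevention. Subtracting a further effect could then count it twice. That stands too, and it is why the figures are given only as an illustration.

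A reader might infer three stronger points that the documents do not support:

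- That the trial claims to compare Ingaron with placebo or with no prevention. No objective, hypothesis or design statement says so. Those phrases appear only as reasons for choosing one-sided or two-sided tests, and the control is openly defined as non-use of the study drug.
- That the comparator is named in three incompatible ways. The phrase "14% of the control group taking alternative methods of protection" describes controls in the literature that the Protocol cites, not Group II.
- That the off-label exception under Concomitant therapy contradicts the Group II rule. That exception qualifies treatment of chronic diseases; preventive drugs have their own heading.

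**Conclusion.** The point holds and should be fixed. The arm-specific rules are explicit, and the contrast they create is Ingaron as the only drug prophylaxis against no interferon gamma with any other participant-chosen drug prophylaxis allowed. The objectives and SAP hypotheses do not say this. The two sidedness rationales presuppose comparators that the Prohibited therapy section does not create: the trial has no placebo and no arm kept free of prevention.

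The size cannot be settled from the documents. At 286 per arm, two-sided 5%, and with 5% read as the rate without other drugs, the examples run from no loss of power (ineffective products) through 48% (10% use, 20% efficacy) to 24% (50% use, 50% efficacy), against about 50% with no such use. Whatever the uptake, the meaning of the result needs stating. If the other products work, a null result cannot be read as no effect of Ingaron.

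**What to change.** The sponsor should reconcile the two arm-specific rules under Prohibited therapy with the Protocol's Objectives and Number of participants sections and with SAP 3.1, 5.1 and 5.2. Which medication rule should apply is for the sponsor; this review does not say which is right.

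If the asymmetry stays:

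- State the contrast in those sections as Ingaron as the only drug prophylaxis versus no interferon gamma, with any other participant-chosen drug prophylaxis allowed.
- Remove the no-prevention rationale (Protocol, Number of participants) and the placebo rationale (SAP 5.2). The choice of sidedness will then need a reason that fits the actual comparator.
- Limit the report's conclusion to that contrast.

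If the asymmetry stays, these are wording changes only. The price is a narrower claim.

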- to evaluate the safety of the proposed regimen of preventive therapy with Ingaron (INN: human recombinant interferon gamma, lyophilizate for the preparation of solution for intranasal administration of 100,000 IU) in adult volunteers. Safety is assessed based on adverse events, clinically significant changes in laboratory parameters during the study, taking into account the assessment of severity according to the STCAE 4.03 scale.

OBJECTIVES OF NON-INTERVENTIONAL RESEARCH

Primary objective

To evaluate the effectiveness of the prophylactic use of Ingaron (INN: human recombinant interferon gamma, lyophilizate for the preparation of solution for intranasal administration of 100,000 IU) in the mode of 3 drops in each nasal passage intranasally every other day for 10 days with break of 7 days (2 10-day cycles) in adult volunteers.

Secondary objectives

Safety assessment of the prophylactic use of Ingaron (INN: human recombinant interferon gamma; lyophilizate for the preparation of a solution for intranasal administration of 100,000 IU), applied 3 drops into each nasal passage intranasally every other day for 10 days with break of 7 days (two 10-day cycles) in adult volunteers.

Efficacy and safety include evaluation based on epidemiological, anamnestic, and clinical data, as well as laboratory studies and specialized scales.

DESIGN OF A NON-INTERVENTIONAL STUDY

Post-marketing prospective randomized open-label comparative non-interventional study in parallel groups.

A total of 4 visits are planned (0–3). Visit 0 and 1 can be combined.

Main stages of the study

1. Visit 0. Conducted in person⁷. Screening: informed consent, inclusion of volunteers and distribution into groups (Day -3-1)
2. Visit 1. Conducted in person. Randomization. Delivery of the investigated drug and the diary of the researcher participant (Day 0)
3. Visit 2. It is carried out remotely (by phone). Completion of a preventive course, evaluation of preventive efficacy and safety during the period of drug administration. The beginning of the observation period. (Day 28–30)
4. Visit 3. Conducted in person. Completion of the observation and research period. (Day 56–62)

The main procedures and stages of the study are reflected in the Schedule of research procedures.

The total duration of participation is about 2 months (56–62 days).

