For participants who have a case of ARVI (COVID-19), visit 3 can be carried out earlier or later, but the total duration of the study should not be more than 90 days. Up to this point, medical researcher should try to collect the most complete information about the patient's condition. If it is not possible to conduct a face-to-face visit, final visit is conducted remotely.

Schedule of research procedures

| Visit number | 0 | 1 | 2 | 3 |
|---|-----------|---------------|--|--|
| Setting | In person | In person | Phone call | In person |
| Visit name | Screening | Randomization | The end of the course of prevention Beginning of the observation period | End of the observation period Completion of the study |
| Study days | -3-1(0) | 0 | 27 (+/-3) | 56-62* |
| Informed consent ¹ | + | | | |
| Anamnesis ² | + | | | |
| Complaints | + | + | + | + |
| Physical examination ³ | + | + | | + |
| Pregnancy test | + | | | |
| Safety assessment | + | + | + | + |
| Analysis for RNA to SARS-CoV-2 ⁴ | + | | | + |
| Checking the inclusion/non-inclusion criteria | + | + | | |
| Checking exclusion criteria | | | + | |

⁷ A full-time visit can be carried out both at the research center and at home

| | | | | |
|--|---|---|---|----------------|
| Randomization | | + | | |
| Delivery of the study drug ⁵ | | + | | + |
| Compliance assessment | | | + | + |
| Issue of the participant's diary | | + | | |
| Effectiveness evaluation | | | + | + |
| Assessment of the participant's condition according to the WHO scale | + | + | + | + ⁷ |
| Return of study drug and diary | | | | + |

* For patients with a registered case of ARVI, duration of participation in the study may be longer, but not exceed 90 days

- 1 All research procedures, except routine laboratory and instrumental studies, the data of which are used to assess the condition of the study participant, are performed after the procedure of signing the informed consent of the patient
- 2 The study should indicate the epidemiological history of respiratory viral diseases, status of vaccination (influenza, pneumonia, COVID-19), use of means of nonspecific protection and prevention of acute respiratory viral infections, including COVID-19

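### Exclusion rules that fall mainly on Group I end study participation, and nothing provides for ARVI outcomes afterwards, so ITT can lack outcomes unequally by arm, chiefly at 2 months

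*Protocol*

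**What the plan says.** Protocol, Exclusion criteria, opens with "A participant should be excluded from the study if at least one of the following criteria is met" and lists ten criteria. They divide as follows.

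- **Group I by label:** criterion 5, "Development of individual intolerance to the study drug (for the study group"), and criteria 7 and 9, each limited to events "in the period before the last intake of the second 10-day cycle (for the study group").
- **Group I by nature:** criterion 3, "Compliance to the study therapy is 50% or less". The Compliance assessment section scores completed courses of the drug, which Group II does not take.
- **Wider in Group I:** criterion 1, use of prohibited therapy. Under Prohibited therapy, "For the study group: use of any medications that may or may have preventive effects against ARVI, including COVID-19, is" prohibited; in the control group only interferon gamma is.
- **Both arms:** criteria 2, 4, 6, 8 and 10. None is specific to control.

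The same section says that excluded participants are not replaced. The only follow-up it describes after exclusion is for pregnancy.

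On timing, the Schedule of research procedures marks "Checking exclusion criteria" at Visit 2 only. Visit 2 is also where Main stages of the study places "evaluation of preventive efficacy and safety during the period of drug administration".

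On analysis, SAP 5.1 makes ITT the main analysis, and SAP 5.5 defines that set without regard to adherence. SAP 5.3 and the protocol's missing-data section restrict analysis to observed data, with no imputation.

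**The concern.** An ITT comparison keeps the protection of randomisation only if outcomes are sought from everyone randomised, whatever happened to their treatment. Here the rules for leaving the study differ by arm, in an open-label trial. A participant who takes another preventive medicine must leave if in Group I and may stay if in Group II. If leaving also ends outcome collection, the observed Group I is a selected part of the randomised group, while Group II is closer to intact.

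Whether that matters depends on whether those excluded differ in ARVI risk. There are plausible routes, though the documents state none. People who feel more exposed may reach for another preventive drug, or illness may interrupt dosing. If those lost are at higher risk than the rest, Group I looks better than it is; if at lower risk, it looks worse. The plan has no analysis that would test this.

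**Working it through.** **1. Do the documents cover outcomes after exclusion?** Four places come close.

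- Under Main stages of the study, the "medical researcher should try to collect the most complete information about" the patient's condition. This concerns participants who have an ARVI case.
- The protocol keeps a participant in the study after a positive PCR during or after the course (end of the Nasopharyngeal smear section). It does not mention people who meet an exclusion criterion.
- SAP 5.1 collects case data throughout the study. For an excluded person the study may already be over.
- Serious adverse events are followed to resolution. That is safety follow-up, not ARVI status.

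So no provision covers ARVI outcomes after exclusion.

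**2. The plan's own figure.** With control risk 5% and Group I risk 2% (Protocol, Number of participants), the protocol formula gives n = (0.05×0.95 + 0.02×0.98)×1.96² / 0.03² = 286.4, stated as 286. Then 286×1.10 = 314.6, stated as 315. The allowance is 315 − 286 = 29 per arm, covering exclusions and consent withdrawals together.

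**3. Effect on the observed day-28 rate.** Assume no drug effect, true risk p = 5% in both arms, L outcomes lost in Group I, none lost in Group II, and risk r among those lost. The documents supply neither L nor r. I take L = 16 for illustration and L = 29 (the whole allowance) as an extreme.

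Observed Group I rate = (315p − Lr)/(315 − L).

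For example, with L = 16 and r = 10%: (15.75 − 1.6)/299 = 4.73%.

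| r | L = 16 | L = 29 |
|---|---|---|
| 0% | 5.27% | 5.51% |
| 5% | 5.00% | 5.00% |
| 10% | 4.73% | 4.49% |
| 15% | 4.46% | 3.99% |

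Group II shows 5.00% throughout.

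**4. Effect on false-positive findings.** I enumerated both binomial distributions under the SAP 5.1 test rule (Fisher if the smallest expected count is below 5, Yates-corrected chi-squared from 5 to 10, Pearson otherwise; two-sided 0.05). The table gives the chance of a significant result favouring the drug.

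| r | L = 16 | L = 29 |
|---|---|---|
| 0% | 1.7% | 1.3% |
| 5% | 2.4% | 2.5% |
| 10% | 3.4% | 4.6% |
| 15% | 4.6% | 8.1% |

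With no loss it is 2.5%. If Group II also loses 8, at the same r, the L = 16 figures at r = 10% and 15% fall to 2.8% and 3.3%.

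**5. If the planned effect is real.** Expected cases are about 6 (2% of 315 = 6.3) against 16 (5% of 315 = 15.75). With complete data, 6/315 against 16/315 gives p = 0.030. With 16 non-cases lost from Group I, 6/299 against 16/315 gives p = 0.041. With 15 non-cases and one case lost, 5/299 against 16/315 gives p = 0.020. Loss of this size does not by itself overturn the planned effect.

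**6. Two months.** The documents give no 2-month rate. At an assumed 10% with 29 outcomes lost in Group I, the observed rate is (31.5 − 29r)/286: 11.0%, 10.0%, 9.0% and 8.0% at r = 0%, 10%, 20% and 30%.

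**The case against.** The best defence is timing. The only scheduled exclusion check is at the contact that also assesses effectiveness, so many excluded participants will already have a day-28 outcome. Criterion 3 in particular rests on compliance scored at Visits 2 and 3. For someone who takes both cycles, scoring 50% or less needs at least two violations in each course, which cannot be established until the second is under way. This stands, and it narrows the primary-endpoint exposure to exclusions acted on mid-course, mainly under criteria 1, 5, 6, 7 and 9. It does nothing for the 2-month endpoints, because Visit 3 comes after the check.

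It is also fair that the illustration is one-sided. Five criteria, including consent withdrawal, apply to both arms, and loss in Group II shrinks the effect (step 4). The loss of 16 is an assumption.

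Two stronger readings are tempting and not supported.

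- A reader might infer that the planned tables would hide unknown outcomes, since SAP Table 8 has only ill and not-ill rows. Under the observed-data rule, the number unknown can be found by subtracting the totals in Tables 8 and 10 from the randomised counts in Table 1. It would be hidden only if unknowns were counted as not ill, and nothing says they are.
- A reader might infer that the per-protocol set drops Group I participants whose course was cut short by ARVI. Nothing requires that, and the protocol keeps PCR-positive participants in. Judging compliance only on doses due before onset would be no remedy, because it would make membership of the set depend on the outcome.

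**Conclusion.** The point holds, as something to fix rather than a fatal flaw. The protocol removes people from the study under rules that bear mainly on Group I, and neither document keeps their ARVI outcomes. The ITT set can therefore fall short of its own definition, unequally by arm.

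Exposure is greatest for the 2-month secondary endpoints. Its size there cannot be estimated from the documents, which give no rate for that time. For the day-28 primary endpoint the effect is small and of unknown direction: a 1.7% to 4.6% chance of a false result favouring the drug, against 2.5%, in the L = 16 illustration. That rests on the assumed 5% risk, loss in one arm only, and risk among those lost between 0% and 15%. The larger figures for 29 losses require the entire allowance to fall on Group I before day 28. If loss is unrelated to ARVI risk there is no bias. The documents therefore do not support a conclusion that the primary result would be materially biased, or biased towards the drug.

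**What to change.** - State in the protocol that meeting an exclusion criterion does not end outcome follow-up. Keep every randomised participant who has not withdrawn consent in the planned Visit 2 call and Visit 3, and analyse them in ITT by assigned group. The rules for stopping the drug stay with the sponsor.
- Report unknown outcomes by arm at day 28 and 2 months, beside the exclusions by criterion already planned in SAP Table 1.
- Add a sensitivity analysis counting missing outcomes as cases and as non-cases. Its worst case is wide when events are few: 6/299 with 16 unknowns becomes 22/315 (7.0%) against 16/315 (5.1%). Follow-up is therefore the main remedy.

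The cost is protocol and SAP wording, one extra analysis, and planned contacts kept for fewer than 58 people (2 × 29, less consent withdrawals). The SAP describes randomisation and adverse-event recording in the past tense. If follow-up has already ended, the reporting and the sensitivity analysis remain possible.

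Separately, reconcile two inconsistencies. Number of participants treats per-protocol as the primary analysis set, whereas Populations for analysis and SAP 5.1 use FAS/ITT. Main stages of the study puts Visit 2 on days 28–30, whereas the Schedule allows day 27 ± 3, that is days 24–30, so a call could precede day 28.
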